#### **4.5 Exploratory Objectives**

##### 4.5.1 Biomarker Research

PD-L1 expression will be tested in tumor specimens to investigate correlations to immune response from treatment with pembrolizumab.

Other exploratory objectives will further describe immune changes resulting from neoadjuvant pembrolizumab +/- SRT. These will include: changes in the number of infiltrating T cell subsets; change in the intratumoral T-cell repertoire by TCR sequencing and single-cell T-cell profiling; and treatment-induced changes in the circulating T cell immune response using TCR sequencing and enzyme-linked immunospot (ELISPOT) assays.

### **5.0 METHODOLOGY**

#### **5.1 Entry Criteria**

##### 5.1.1 Diagnosis/Condition for Entry into the Trial

1. Histologically or cytologically confirmed non-small cell lung cancer, performed on a biopsy that occurred within the last 120 days.
2. PET-CT within the last 75 days showing radiographic stage I to IIIa lung cancer (mediastinal staging biopsy is allowed but not required).
3. Documentation that the patient is a candidate for surgical resection of their lung cancer by an American Board of Thoracic Surgery-certified surgeon.
4. Measurable disease as defined by RECIST v1.1.
5. Adequate tissue specimens for correlative biomarker analysis. The patient should be willing to provide tissue from a newly obtained core or excisional biopsy of a tumor lesion. Newly-obtained is defined as a specimen obtained up to 120 days prior to initiation of treatment on Day 1. Subjects for whom newly-obtained samples cannot be provided (e.g. inaccessible or subject safety concern) may submit an archived specimen only upon agreement from the Principal Investigator.
6. Eastern Cooperative Oncology Group (ECOG) performance status of 0 to 1.
7. Resolution of all acute toxic effects of prior chemotherapy, radiotherapy or surgical procedures to NCI CTCAE Version 4.0 grade 1.

##### 5.1.2 Subject Inclusion Criteria

In order to be eligible for participation in this trial, the subject must:

1. Be willing and able to provide written informed consent/assent for the trial.
2. Be  $\geq 18$  years of age on day of signing informed consent.
3. Demonstrate adequate organ function as defined in Table 1. All screening labs should be performed within 10 days of treatment initiation, unless specified below.

Table 1 Adequate Organ Function Laboratory Values

System	Laboratory Value
Hematological	
Absolute neutrophil count (ANC)	$\geq 1,500 / \text{mcL}$
Platelets	$\geq 100,000 / \text{mcL}$
Hemoglobin a	$\geq 9 \text{ g/dL}$ or $\geq 5.6 \text{ mmol/L}$
Renal	
Serum creatinine OR Measured or calculated b creatinine clearance (GFR can also be used in place of creatinine or CrCl)	$\leq 1.5 \times \text{upper limit of normal (ULN)}$ OR $\geq 60 \text{ mL/min}$ for subject with creatinine levels $> 1.5 \times \text{institutional ULN}$
Hepatic	
Serum total bilirubin	$\leq 1.5 \times \text{ULN}$
AST (SGOT) and ALT (SGPT)	$\leq 2.5 \times \text{ULN}$
Coagulation	
International Normalized Ratio (INR) or Prothrombin Time (PT)	$\leq 1.5 \times \text{ULN}$ unless subject is receiving anticoagulant therapy as long as PT or PTT is within therapeutic range of intended use of anticoagulants
Activated Partial Thromboplastin Time (aPTT)	$\leq 1.5 \times \text{ULN}$ unless subject is receiving anticoagulant therapy as long as PT or PTT is within therapeutic range of intended use of anticoagulants

aPatients cannot have received transfusion or erythropoietin (EPO) within 7 days of the hemoglobin (Hgb) lab test as this may artificially inflate the Hgb lab value.
 
bCreatinine clearance should be calculated per institutional standard.
	

4. Female subject of childbearing potential should have a negative urine or serum pregnancy within 72 hours prior to receiving the first dose of study medication. If the urine test is positive or cannot be confirmed as negative, a serum pregnancy test will be required.
5. Female subjects of childbearing potential (Section 5.7.2) must be willing to use an adequate method of contraception, as outlined in Section 5.7.2 – Contraception, for the course of the study through 120 days after the last dose of study medication.  
Note: Abstinence is acceptable if this is the usual lifestyle and preferred contraception for the subject.
6. Male subjects of childbearing potential (Section 5.7.1) must agree to use an adequate method of contraception as outlined in Section 5.7.1- Contraception, starting with the first dose of study therapy through 120 days after the last dose of study therapy.  
Note: Abstinence is acceptable if this is the usual lifestyle and preferred contraception for the subject.

### 5.1.3 Subject Exclusion Criteria

The subject must be excluded from participating in the trial if the subject:

1. Is ineligible for an operation based on medical or oncologic contraindications to surgery.
2. Has a history of (non-infectious) pneumonitis/interstitial lung disease that required steroids or has current pneumonitis/interstitial lung disease.
3. Has evidence of interstitial lung disease.
4. Has an active second malignancy, i.e. patient known to have potentially fatal cancer present for which he/she may be (but not necessarily) currently receiving treatment. Patients with a history of malignancy that has been completely treated, with no evidence of that cancer currently, are permitted to enroll in the trial if curative therapy has been completed, such as basal cell carcinoma of the skin or squamous cell carcinoma of the skin that has undergone potentially curative therapy or in situ cervical cancer.
5. Is currently participating and receiving study therapy or has participated in a study of an investigational agent and received study therapy or used an investigational device within 4 weeks of the first dose of treatment.
6. Has a diagnosis of immunodeficiency or is receiving systemic steroid therapy or any other form of immunosuppressive therapy within 7 days prior to the first dose of trial treatment.
7. Has a known history of active TB (Bacillus Tuberculosis)
8. Hypersensitivity to pembrolizumab or any of its excipients.
9. Has had a prior anti-cancer monoclonal antibody (mAb) within 4 weeks prior to study Day 1 or who has not recovered (i.e.,  $\leq$  Grade 1 or at baseline) from adverse events due to agents administered more than 4 weeks earlier.
10. Has had prior chemotherapy, targeted small molecule therapy, or radiation therapy within 2 weeks prior to study Day 1 or who has not recovered (i.e.,  $\leq$  Grade 1 or at baseline) from adverse events due to a previously administered agent.
  - Note: Subjects with  $\leq$  Grade 2 neuropathy are an exception to this criterion and may qualify for the study.
  - Note: If subject received major surgery, they must have recovered adequately from the toxicity and/or complications from the intervention prior to starting therapy.
11. Has active autoimmune disease that has required systemic treatment in the past 2 years (i.e. with use of disease modifying agents, corticosteroids or immunosuppressive drugs). Replacement therapy (eg., thyroxine, insulin, or physiologic corticosteroid replacement therapy for adrenal or pituitary insufficiency, etc.) is not considered a form of systemic treatment.

12. Has an active infection requiring systemic therapy.
13. Has a history or current evidence of any condition, therapy, or laboratory abnormality that might confound the results of the trial, interfere with the subject's participation for the full duration of the trial, or is not in the best interest of the subject to participate, in the opinion of the treating investigator.
14. Has known psychiatric or substance abuse disorders that would interfere with cooperation with the requirements of the trial.
15. Is pregnant or breastfeeding, or expecting to conceive or father children within the projected duration of the trial, starting with the pre-screening or screening visit through 120 days after the last dose of trial treatment.
16. Has received prior therapy with an anti-PD-1, anti-PD-L1, or anti-PD-L2 agent.
17. Has a known history of Human Immunodeficiency Virus (HIV) (HIV 1/2 antibodies).
18. Has known active Hepatitis B (e.g., HBsAg reactive) or Hepatitis C (e.g., HCV RNA [qualitative] is detected).
19. Has received a live vaccine or live-attenuated vaccine within 30 days prior to the first dose of the study drug. Administration of killed vaccines is allowed.

*Note: Seasonal influenza vaccines for injection are generally inactivated flu vaccines and are allowed; however intranasal influenza vaccines (e.g., Flu-Mist®) are live attenuated vaccines, and are not allowed.*

## **5.2 Trial Treatments**

The treatment to be used in this trial is outlined below in Table 2.

**Table 2 Trial Treatment**

Drug	Dose/Potency	Dose Frequency	Route of Administration	Regimen/Treatment	Use
Pembrolizumab	200 mg	Q3W	IV infusion	Day 1 of each 3-week cycle	Experimental

Stereotactic radiation therapy will be given at a prescription dosage of 12 Gy at the 80% isodose line, to be delivered in one single treatment session in one day, to 50% +/- 10% of the primary tumor volume, as determined by volumetric measurement of the total tumor volume and the volume of that tumor within the prescribed planning target volume (PTV). The lateral half of the tumor should be encompassed within the PTV and the medial aspect of the tumor relative to the patient should not be included in the PTV. Treatment may be delivered from either a linear accelerator or robotic SRT delivery system. SRT, if the patient is to receive it according to the terms of the protocol, should be given within 7 days (+/- 3 days) following the second administration of pembrolizumab. If the second cycle is not given, then SRT should not be given.

During dose expansion, trial treatment should begin on the day of randomization or as close as possible to the date on which treatment is allocated/assigned.

### 5.2.1 Dose Selection/Modification

#### 5.3.2.1 Dose Selection

The rationale for selection of doses to be used in this trial is provided in Section 4.0 – Background and Rationale.

Details on preparation and administration of pembrolizumab (MK-3475) are provided in the Pharmacy Manual.

##### 5.2.1.1 Dose Modification (Escalation/Titration/Other)

Adverse events (both non-serious and serious) associated with pembrolizumab exposure, including coadministration with additional compounds, may represent an immunologic etiology. These adverse events may occur shortly after the first dose or several months after the last dose of pembrolizumab/combination and may affect more than one body system simultaneously. Pembrolizumab/combination treatment must be withheld for drug-related toxicities and severe or life-threatening AEs as per Table 3 below. See Section 5.6 for supportive care guidelines, including use of corticosteroids.

If a patient continues to experience toxicity, or if dosing with study drug is interrupted for > 14 consecutive days due to toxicity, treatment should be discontinued unless otherwise agreed between the investigators before reintroduction of study drug.

The following dose modification rules will be used with respect to potential toxicity. Toxicity will be assessed according to the NCI Common Terminology Criteria for Adverse Events [Version 4.0 \(CTCAE v4.0\)](#).

#### Attribution of Toxicity:

When study interventions are administered in combination, attribution of an adverse event to a single component is likely to be difficult. Therefore, while the investigator may attribute a toxicity event to the combination, to stereotactic radiotherapy, or to pembrolizumab alone, for adverse events listed in Table 3, both interventions must be held according to the criteria in Table 3 Dose Modification and Toxicity Management Guidelines for Immune-Related Adverse Events Associated with Pembrolizumab.

#### Holding Study Interventions:

When study interventions are administered in combination, if the AE is considered immune-related, both interventions should be held according to recommended dose modifications.

#### Restarting Study Interventions:

Participants may not have any dose modifications (no change in dose or schedule) of pembrolizumab in this study, as described in Table 3.

- If the toxicity does not resolve or the criteria for resuming treatment are not met, the participant must be discontinued from all study interventions.

If the toxicities do resolve and conditions are aligned with what is defined in Table 3, the combination of stereotactic radiotherapy and pembrolizumab may be restarted at the discretion of the investigator. In these cases where the toxicity is attributed to the combination or to stereotactic radiotherapy alone, re-initiation of pembrolizumab as a monotherapy may be considered at the principal investigator's discretion.

**Table 3 Dose Modification and Toxicity Management Guidelines for Immune-Related AEs associated with pembrolizumab monotherapy and IO Combinations**

## General instructions:

1. Severe and life-threatening irAEs should be treated with IV corticosteroids followed by oral steroids. Other immunosuppressive treatment should begin if irAEs are not controlled by corticosteroids.
2. Study intervention must be permanently discontinued if the irAE does not resolve or the corticosteroid dose is not  $\leq$ 10 mg/day within 12 weeks of the last study intervention treatment.
3. The corticosteroid taper should begin when the irAE is  $\leq$  Grade 1 and continue at least 4 weeks.
4. If study intervention has been withheld, study intervention may resume after the irAE decreased to  $\leq$  Grade 1 after corticosteroid taper.

irAEs	Toxicity Grade (CTCAE v5.0)	Action with pembrolizumab	Corticosteroid and/or other therapies	Monitor and Follow-up
Pneumonitis	Grade 2	Withhold	
 
• Administer corticosteroids (initial dose of 1 to 2 mg/kg prednisone or equivalent) followed by taper
 
• Add prophylactic antibiotics for opportunistic infections
 
	
 
• Monitor participants for signs and symptoms of pneumonitis
 
• Evaluate participants with suspected pneumonitis with radiographic imaging and initiate corticosteroid treatment
 

	Recurrent Grade 2, Grade 3 or 4	Permanently discontinue		
Diarrhea/Colitis	Grade 2 or 3	Withhold	
 
• Administer corticosteroids (initial dose of 1 to 2 mg/kg prednisone or equivalent) followed by taper
 
	
 
• Monitor participants for signs and symptoms of enterocolitis (i.e., diarrhea, abdominal pain, blood or mucus in stool with or without fever) and of bowel perforation (i.e., peritoneal signs and ileus)
 
• Participants with <math>\geq</math>Grade 2 diarrhea suspecting colitis should consider GI consultation and performing endoscopy to rule out colitis
 
• Participants with diarrhea/colitis should be advised to drink liberal quantities of clear fluids. If sufficient oral fluid intake is not feasible, fluid and electrolytes should be substituted via IV infusion
 

	Recurrent Grade 3 or Grade 4	Permanently discontinue		
AST or ALT Elevation or Increased Bilirubin	Grade 2 a	Withhold	
 
• Administer corticosteroids (initial dose of 0.5 to 1 mg/kg prednisone or
 
	
 
• Monitor with liver function tests (consider weekly or more frequently until liver enzyme
 

			equivalent) followed by taper	value returned to baseline or is stable)
	Grade 3 b or 4 c	Permanently discontinue	
 
Administer corticosteroids (initial dose of 1 to 2 mg/kg prednisone or equivalent) followed by taper
 
	
T1DM or Hyperglycemia	New onset T1DM or Grade 3 or 4 hyperglycemia associated with evidence of $\beta$ -cell failure	Withhold d	
 
Initiate insulin replacement therapy for participants with T1DM
 
Administer antihyperglycemic in participants with hyperglycemia
 
	
 
Monitor participants for hyperglycemia or other signs and symptoms of diabetes
 

Hypophysitis	Grade 2	Withhold	
 
Administer corticosteroids and initiate hormonal replacements as clinically indicated
 
	
 
Monitor for signs and symptoms of hypophysitis (including hypopituitarism and adrenal insufficiency)
 

	Grade 3 or 4	Withhold or permanently discontinue d		
Hyperthyroidism	Grade 2	Continue	
 
Treat with nonselective beta-blockers (e.g., propranolol) or thionamides as appropriate
 
	
 
Monitor for signs and symptoms of thyroid disorders.
 

	Grade 3 or 4	Withhold or permanently discontinue 		
Hypothyroidism	Grade 2-4	Continue	
 
Initiate thyroid replacement hormones (e.g., levothyroxine or liothyroinine) per standard of care
 
	
 
Monitor for signs and symptoms of thyroid disorders.
 

Nephritis: grading according to increased creatinine or acute kidney injury	Grade 2	Withhold	
 
Administer corticosteroids (prednisone 1 to 2 mg/kg or equivalent) followed by taper.
 
	
 
Monitor changes of renal function
 

	Grade 3 or 4	Permanently discontinue		
Neurological Toxicities	Grade 2	Withhold	
 
Based on severity of AE administer corticosteroids
 
	
 
Ensure adequate evaluation to confirm etiology and/or exclude other causes
 

	Grade 3 or 4	Permanently discontinue		
Myocarditis	Grade 1 or 2	Withhold	
 
Based on severity of AE administer corticosteroids
 
	
 
Ensure adequate evaluation to confirm etiology and/or exclude other causes
 

	Grade 3 or 4	Permanently discontinue		
Exfoliative	Suspected SJS, TEN, or	Withhold		

Dermatologic Conditions	DRESS		
 
Based on severity of AE administer corticosteroids
 
Ensure adequate evaluation to confirm etiology or exclude other causes
 

	Confirmed SJS, TEN, or DRESS	Permanently discontinue	
All other irAEs	persistent Grade 2	Withhold	
 
Based on severity of AE, administer corticosteroids
 
Ensure adequate evaluation to confirm etiology and/or exclude other causes
 

	Grade 3	Withhold or discontinue based on the event e . Events that require discontinuation include and not limited to: Gullain-Barre Syndrome, encephalitis	
	recurrent Grade 3 or Grade 4	Permanently discontinue	

AE(s)=adverse event(s); ALT= alanine aminotransferase; AST=aspartate aminotransferase; CTCAE=Common Terminology Criteria for Adverse Events; DRESS=Drug Rash with Eosinophilia and Systemic Symptom; GI=gastrointestinal; IO=immuno-oncology; ir=immune related; IV=intravenous; SJS=Stevens-Johnson Syndrome; T1DM=type 1 diabetes mellitus; TEN=Toxic Epidermal Necrolysis; ULN=upper limit of normal.

**Note: Non-irAE will be managed as appropriate, following clinical practice recommendations.**

a AST/ALT: >3.0 to 5.0 x ULN if baseline normal; >3.0 to 5.0 x baseline, if baseline abnormal;

bilirubin:>1.5 to 3.0 x ULN if baseline normal; >1.5 to 3.0 x baseline if baseline abnormal

b AST/ALT: >5.0 to 20.0 x ULN, if baseline normal; >5.0 to 20.0 x baseline, if baseline abnormal; bilirubin:>3.0 to 10.0 x ULN if baseline normal; >3.0 to 10.0 x baseline if baseline abnormal

c AST/ALT: >20.0 x ULN, if baseline normal; >20.0 x baseline, if baseline abnormal;

bilirubin: >10.0 x ULN if baseline normal; >10.0 x baseline if baseline abnormal

d The decision to withhold or permanently discontinue pembrolizumab is at the discretion of the investigator or treating physician. If control achieved or  $\leq$  Grade 2, pembrolizumab may be resumed.

e Events that require discontinuation include, but are not limited to: encephalitis and other clinically important irAEs.

1. Withhold or permanently discontinue pembrolizumab is at the discretion of the investigator or treating physician.

**NOTE:** For participants with Grade 3 or 4 immune-related endocrinopathy where withhold of pembrolizumab is required, pembrolizumab may be resumed when AE resolves to  $\leq$  Grade 2 and is controlled with hormonal replacement therapy or achieved metabolic control (in case of T1DM).

Dosing interruptions are permitted in the case of medical / surgical events or logistical reasons not related to study therapy (e.g., elective surgery, unrelated medical events, patient vacation, and/or holidays). Subjects should be placed back on study therapy within 3 weeks of the scheduled interruption, unless otherwise discussed with the Principal Investigator. The reason for interruption should be documented in the patient's study record.

#### 5.2.2 Timing of Dose Administration

Trial treatment should be administered on Day 1 of each cycle after all procedures/assessments have been completed as detailed on the Trial Flow Chart (Section 6.0). Trial treatment may be administered up to 3 days before or after the scheduled Day 1 of each cycle due to administrative reasons.

All trial treatments will be administered on an outpatient basis.

Pembrolizumab 200 mg will be administered as a 30-minute IV infusion every 3 weeks, for 2 cycles. Sites should make every effort to target infusion timing to be as close to 30 minutes as possible. However, given the variability of infusion pumps from site to site, a window of -5 minutes and +10 minutes is permitted (i.e., infusion time is 30 minutes: -5 min/+10 min).

The Pharmacy Manual contains specific instructions for the preparation of the pembrolizumab infusion fluid and administration of infusion solution.

#### 5.2.3 Trial Blinding/Masking

This trial is open label; therefore, the subject, the trial site personnel, the Principal Investigator and/or designee are not blinded to treatment.

### **5.3 Randomization or Treatment Allocation**

For the run-in cohorts, consecutive patients will be enrolled.

In the expansion cohort, consecutive patients will be enrolled if only Cohort 1 conditions are fulfilled. If Cohort 1 and Cohort 2 both meet safety criteria, then patients will be enrolled in the Expansion Cohort using permuted-block randomization with block size of 4.

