## 2.0 TRIAL DESIGN

### 2.1 Trial Design

This is a randomized single-institution, phase II, open-label clinical trial of neoadjuvant pembrolizumab with or without low-dose stereotactic radiation therapy (SRT) in stage I- IIIA non-small lung cancer (NSCLC) patients who are planned to undergo surgical resection of their lung cancer.

Two consecutive run-in cohorts will administer pembrolizumab or pembrolizumab with SRT of 12 Gy to the lateral aspect of the primary tumor. Patients will receive pembrolizumab for 2 cycles prior to surgery or SRT and surgery. Surgical resection of all involved areas of tumor will occur within 6 weeks of the last administration of pembrolizumab. It should be noted that in almost all cases, surgery is expected to occur very expeditiously, within a much shorter window and 6 weeks would represent only the greatest allowable amount of delay.

If during the run-in, only the pembrolizumab-alone cohort meets pre-specified safety parameters, subsequently enrolled patients will enter a larger expansion cohort, with treatment given according to that cohort only. If during the run-in both cohorts meet pre-specified safety parameters, subsequently enrolled patients will enter the expansion cohort and be randomized between preoperative pembrolizumab versus pembrolizumab with SRT of 12 Gy.

Patients will be followed every 12 weeks for 1 year for disease status and survival.

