**Expansion Cohort:** 28 patients. The patients will be treated according to Cohort 1 if Cohort 2 failed to meet the specified safety milestones. If both cohorts met the safety milestones, then patients in this cohort will be randomized to parameters of either Cohort 1 or Cohort 2. Surgery will occur no later than 6 weeks following the last dose of pembrolizumab.

**Stopping Rule:** If at any point during the study, >15% of patients progress to unresectability over the course of the study treatment, then the study will terminate. This stopping rule will be cumulatively evaluated at all timepoints during the protocol, for all patients enrolled in any phase of the protocol. Each case of study-induced medical unfitness, tumor progression, or any other cause resulting in unresectability will trigger a re-evaluation of the 15% stopping rule.

\* Cycle 2 of pembrolizumab should be given except as recommended per protocol, section 5.2.1.2

\*\* SRT is delivered within 7 days +/- 3 days of second pembrolizumab cycle. If second cycle is not given due to discontinuation, SRT should not be given (patient should continue to surgery)

when deemed safe by treating surgeon).

^ Surgery will take place no later than 6 weeks following last dose of pembrolizumab, e.g. no later than week 7 if only one cycle of pembrolizumab was tolerated, or if two cycles of pembrolizumab were given, week 10.

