### **5.4 Stratification**

No stratification is to be performed.

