#### 7.2 Statistical Analysis Plan

Sample size justification:

The sample size is based upon the anticipated number of patients who will have samples that will be useful for study of immunologic changes in the number of infiltrating CD3+ T cells/ $\mu\text{m}^2$  in the lung cancer tissue between the pre-treatment (baseline) biopsy and post-treatment thoracotomy specimens.

The sample size is fixed at 40 patients. It assumes successful accrual of 6 patients from each of the two run-in cohorts and an additional 28 patients from the randomized expansion cohort, for a total of 40 patients. However, past clinical experience indicates that as many as one-third of patients may not be able to complete a new successful core needle biopsy procedure and only prior archived tissues will be available for any analysis (which may eventually turn out to be insufficient to evaluate for primary endpoint). These patients who enrolled but whose core biopsy is later found to be inadequate after initiation of therapy will be allowed to continue on the protocol but will not be included in the primary endpoint.

The null hypothesis is that a two-fold increase will be seen in 15% of the evaluable 26 patients (assuming up to one third of samples may be unevaluable for primary endpoint). The alternative hypothesis is that a two-fold increase will be seen in 40% of the evaluable 26 patients. This yields 90% statistical power, with one sided 5% alpha level based on an exact binomial test.

The goal of achieving a two-fold increase in 40% of the evaluable population is a reasonable one, as estimated from a previous study showing greater-than-three-fold increase in 57% of patients when CD3+ T cells/ $\mu\text{m}^2$  were measured in prostate cancer tissue treated with a cell- based cancer immunotherapy, with a null hypothesis having been set at a two-fold increase in 15% of the population (Fong 2014). The current study includes immunotherapy +/- stereotactic radiation therapy, both of which are anticipated to create increased immunogenicity against NSCLC.

It is anticipated that accrual will be completed in 10 months (4 patients per month), with each patient treated for approximately 2.5-3 months and then followed for 12 months after completing protocol therapy. Total study duration is 25 months.

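### If the expansion cohort is randomised, a printed fixed block size of 4 with no described concealment makes on average one third of its allocations (1:1 assumed) knowable beforehand to staff who track earlier assignments

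*Combined protocol and SAP*

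**What the plan says.** Section 5.3 makes randomisation conditional: "If Cohort 1 and Cohort 2 both meet safety criteria, then patients will be enrolled in the Expansion Cohort" by "permuted-block randomization with block size of 4". If only Cohort 1 passes, expansion patients are enrolled consecutively on one treatment and nobody is randomised. Section 2.2 gives the two arms: "patients in this cohort will be randomized to parameters of either Cohort 1 or Cohort 2". Section 7.2 gives the number: "an additional 28 patients from the randomized expansion cohort". No allocation ratio is stated for this trial.

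Three other provisions bear on predictability:

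- Section 2.1: "This is a randomized single-institution, phase II, open-label clinical trial".
- Section 5.2.3: "the subject, the trial site personnel, the Principal Investigator and/or designee are not blinded to treatment".
- Section 5.4: "No stratification is to be performed".

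On the mechanics, section 6.2.1.6 says only that a patient receives a randomisation number when randomised in the expansion phase. The documents do not say who generates or holds the list, or at what point the next assignment becomes visible.

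**The concern.** With one centre and no strata there is a single sequence. Because treatment is open, staff who enrol patients can see every earlier assignment, and the protocol they hold tells them where each block ends. Once one arm has filled its places in a block, the rest of that block is known.

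Entry involves some judgement. A surgeon must document surgical candidacy and the Principal Investigator may agree to archival tissue (section 5.1.1). Exclusion 13 rests on the treating investigator's opinion (section 5.1.3). Screening runs over 28 days (section 6.2.9), which leaves some latitude in when a patient is randomised. Someone who knows the next arm could therefore advance, delay or decline a patient. No intent is alleged; concealment exists to remove the opportunity.

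At stake is the only randomised comparison in the trial. Secondary objectives 3 to 5 in section 3.2 predict better 1-year overall survival, better relapse-free survival and fewer distant metastases with SRT added. Section 4.4 says these data should help decide which program merits further study. Stages I to IIIA are eligible, a wide prognostic range. With about 14 patients per arm and no stratification, a few steered patients could change the stage mix.

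**Working it through.** The plan gives no predictability figure to reproduce, so this is a direct enumeration.

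**Inputs.** Block size 4 (section 5.3); two arms (2.2); one list (2.1, 5.4); past assignments visible (5.2.3); 28 randomised (7.2), which is 28/4 = 7 complete blocks. Assumption: 1:1, so two patients per arm in each block.

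**Certain allocations.** An allocation is certain when every place left in the block belongs to one arm. There are six equally likely sequences:

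- AABB and BBAA: places 3 and 4 are certain (2 each).
- ABAB, ABBA, BAAB and BABA: place 4 only (1 each).

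Mean per block = (2×2 + 4×1)/6 = 4/3, and (4/3)/4 = 33.3%. Over 7 blocks, 7 × 4/3 = 9.33 of 28.

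**Spread.** Each block contributes one certain allocation, plus a second with probability 2/6 = 1/3. The total is therefore 7 + Binomial(7, 1/3). The minimum is 7 (25%) and the maximum 14 (50%), with P(10 or more) = 0.43.

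**Best-guess accuracy.** The guesser always names the arm with more places left. The chance of being right is:

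- place 1: 1/2
- place 2: 2/3
- place 3: 1/3 × 1 + 2/3 × 1/2 = 2/3
- place 4: 1

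The sum is 2.833, and 2.833/4 = 70.8%, or 19.8 of 28. Simple randomisation would give 50%.

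**Sensitivity to the unstated ratio.** The only other two-arm split of a block of 4 is 3:1. Its four sequences have 1, 1, 2 and 3 certain places. The mean is 7/4 per block, so 7/16 = 43.75%.

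**Alternatives over 28 patients at 1:1.** The mixed-size rows are simulated for a guesser who knows the set of sizes but not the current one.

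| Blocks | Certain | Best guess right |
|---|---|---|
| Fixed 4 | 33.3% (9.3 of 28) | 70.8% |
| Fixed 6 | about 22% | about 67% |
| Fixed 8 | about 17% | about 65% |
| Random 4 or 6 | about 6% (1.6 of 28) | about 69% |
| Random 2, 4 or 6 | about 4% (1.1 of 28) | about 70% |

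**Reach.** Section 7.2 plans one exact binomial test of a single proportion against 15%, with 26 evaluable patients assumed out of the 40 enrolled. It specifies no between-arm test. Predictable allocation therefore bears on the comparisons in section 3.2, not on that test.

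**The case against.** The strongest reply is about weight. The trial's one specified test compares no arms. Sections 4.3.4 and 4.4 both describe the 1-year clinical outcomes as exploratory. With about 14 per arm, chance imbalance and sampling error already limit what those comparisons can show. All of this stands, and it confines the point to the secondary comparisons.

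The second reply is that varying the blocks achieves little: a person who wants to steer can act on any better-than-even guess, and accuracy drops by only about two percentage points. On that measure a plain block of 6 or 8 does slightly better, though it leaves more allocations certain. This also stands. The gain from mixed sizes lies in removing certainties, and it does not replace a concealment step.

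The third reply is that there is an audit trail: a screening number separate from the randomisation number (sections 6.2.1.5 and 6.2.1.6), a screening/enrolment log (Appendix 4), and documented surgical candidacy (section 5.1.1). These records help to detect steering afterwards. They do not hide the next allocation.

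A reader might also infer that the primary result is compromised, or that steering has taken place. The documents support neither. The primary test makes no between-arm comparison, and nothing shows that staff track the sequence or that randomisation has begun.

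**Conclusion.** The point holds as an inexpensive improvement to a design choice; it is not an error or a contradiction in the plan. Under the stated rule, at least 7 of the 28 randomised allocations, 9.3 on average and at most 14, can be known before the patient is randomised. No described procedure prevents this.

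The result rests on four conditions:

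- Both run-in cohorts pass. Otherwise there is no randomisation.
- Allocation is 1:1. Under 3:1 the average share would be 43.75%.
- The enroller follows earlier assignments and knows where blocks begin.
- The 28 patients fill complete blocks. Section 5.9 allows replacements but does not say how they enter the sequence.

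Two wider readings should be resisted. One third is an average over the 28 randomised patients, not a fixed share and not a share of the trial: 9.33/40 is 23% of all 40 patients. And certain beforehand means certain given the earlier assignments in the block, not known from the start of the study.

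The consequence is possible selection bias in the between-arm comparisons of 1-year survival, relapse-free survival and distant metastasis. Its size cannot be estimated from the documents.

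**What to change.** In section 5.3, replace the fixed block size with randomly varying block sizes, generated and held by the trial statistician and not disclosed in the protocol. In the same place, require that each assignment be released only after the patient has been irreversibly registered as eligible. State the allocation ratio there too. The release rule belongs alongside the block sizes because varying sizes alone leave guess accuracy near 69%.

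The cost is a new list and an amendment approved by the Protocol Review Committee and the IRB before implementation (section 9.4). The arms may also end slightly unequal. With sizes 4 and 6 and exactly 28 patients, the list can stop only after an even number of places in its last block. The difference is then at most 2, for example 13 versus 15.

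If randomisation has already begun, the change can apply to the remaining assignments. The report should then describe the concealment actually used and show baseline stage by arm.
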